9.2.1 Potential Hy's Law Cases

Total bilirubin level should be checked for any subject with increased ALT or AST levels greater or equal to three times the upper limit of normal (or baseline). If total bilirubin level is greater or equal to twice upper limit of normal (or baseline), IRE form with the lab values will be sent to INC Research within 24 hours. The corresponding pages of the eCRF should be filled.

Reporting all potential cases as SAE to the FDA based on Hy's Law:

- AST or ALT $\geq 3 \times \text{ULN}$ and
- Total Bilirubin $\geq 2 \times \text{ULN}$

A separate incidence table will be provided for Hy's Law cases, and the corresponding listing will be provided.

9.3 Physical Examination and Vital Signs Data

By-patient listings will be provided for physical examination. Summary statistics for changes from baseline in vital signs will be provided. Potentially clinically significant results in vital signs will also be summarized. In addition, the change from baseline in weight, BMI, and waist circumference, and potentially clinically relevant abnormalities in weight, will also be summarized by ADT and by Gender, separately.

9.4 ECG Data

Mean change from baseline and incidence of clinically significant changes will be calculated for ECG parameters.

For the analysis of QT and QTc, data from three consecutive complexes (representing three consecutive heart beats) will be measured to determine average values. The following QT corrections will be used for reporting purposes in the clinical study report:

- 1) QTcB is the length of the QT interval corrected for heart rate by the Bazett formula: $\text{QTcB} = \text{QT}/(\text{RR})^{0.5}$
- 2) QTcF is the length of the QT interval corrected for heart rate by the Fridericia formula: $\text{QTcF} = \text{QT}/(\text{RR})^{0.33}$

3) QTcN is the length of the QT interval corrected for heart rate by the FDA
 Neuropharm Division formula: $QTcN = QT / (RR)^{0.37}$

Categorical changes in ECG parameters will be summarized based on the following criteria:

Table 9.4-1 Categorical Change Criteria in QT/QTc Parameters		
Classification	Category	Criteria
QT	New Onset (> 450 Msec)	New onset (>450 msec) in QT means a subject who attains a value > 450 msec during treatment period but not at baseline.
QTc *	New Onset (> 450 Msec)	New onset (> 450 msec) in QTc means a subject who attains a value > 450 msec during treatment period but not at baseline.
	New Onset (> 450 Msec) And > 10% Increase	New onset (> 450 msec) and > 10% increase in QTc means a subject who attains a value > 450 msec and > 10% increase during treatment period but not at baseline
	New Onset (> 500 Msec)	New onset (> 500 msec) in QTc means a subject who attains a value > 500 msec during treatment period but not at baseline.
	Increase 30 - 60 Msec	Increase from baseline value > 30 and \leq 60 msec in QTc
	Increase > 60 Msec	Increase from baseline value > 60 msec in QTc

* QTc categorical change criteria apply to QTcB, QTcF and QTcN.

9.5 Suicidality Data

Suicidality will be monitored during the study using the C-SSRS and will be summarized as number and percentage of subjects reporting any suicidal behavior, ideation, behavior by type (4 types), ideation by type (5 types) and treatment emergent suicidal behavior and ideation.

Suicidality is defined as report of at least one occurrence of any type of suicidal ideation or at least one occurrence of any type of suicidal behavior during assessment period (count each person only once).

Treatment emergent suicidal behavior and ideation is summarized by four types:

Emergence of suicidal ideation, Emergence of serious suicidal ideation, Worsening of suicidal ideation, Emergence of suicidal behavior.

Emergence of suicidal behavior/ideation is defined as report of any type of suicidal behavior/ideation during treatment when there was no baseline suicidal behavior/ideation.

Emergence of serious suicidal ideation is defined as observation of suicidal ideation severity rating of 4 or 5 during treatment when there was no baseline suicidal ideation.

Worsening of suicidal ideation is defined as a suicidal ideation severity rating that is more severe than it was at baseline.

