7.	Subjects with a current Axis I (DSM-IV-TR) diagnosis of: 
 • Delirium, dementia, amnestic or other cognitive disorder • Schizophrenia, schizoaffective disorder, or other psychotic disorder • Bipolar I or II disorder • Eating disorder (including anorexia nervosa or bulimia) • Obsessive compulsive disorder • Panic disorder • Post-traumatic stress disorder
8.	Subjects with a current Axis II (DSM-IV-TR) diagnosis of borderline, antisocial, paranoid, schizoid, schizotypal or histrionic personality disorder.
9.	Subjects experiencing hallucinations, delusions or any psychotic symptomatology in the current depressive episode.
10.	Subjects receiving new onset psychotherapy (individual, group, marriage, or family therapy) during the prior double-blind phase 3 trial.
Medical History and Concurrent Diseases	
11.	Subjects with a response of “Yes” on the C-SSRS Suicidal Ideation Item 4 (Active Suicidal Ideation with Some Intent to Act, Without Specific Plan) at entry, OR Subjects with a response of “Yes” on the C-SSRS Suicidal Ideation Item 5 (Active Suicidal Ideation with Specific Plan and Intent) at entry, OR Subjects with a response of “Yes” on any of the 5 C-SSRS Suicidal Behavior Items (actual attempt, interrupted attempt, aborted attempt, preparatory acts, or behavior) at entry, OR Subjects who, in the opinion of the investigator (including consideration of responses on the C-SSRS throughout the prior double-blind phase 3 trial), present a serious risk of suicide. Note: “Entry” is defined as the last scheduled visit of the prior double-blind phase 3 trial.
12.	Subjects who have met DSM-IV-TR criteria for substance abuse or dependence within the past 180 days; including alcohol and benzodiazepines, but excluding caffeine and nicotine.
13.	Subjects with hypothyroidism or hyperthyroidism (unless condition has been stabilized with medications for at least the past 90 days) and/or an abnormal result for free T4 at screening/baseline. Eligibility of subjects excluded based on an abnormal free T4 result can be discussed with the medical monitor if, in the investigator’s judgment, the subject is a suitable candidate for the trial.

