3.6.1 Schedule of Assessments

3.6.1.1 Screening/Baseline

Subjects entering Trial 331-10-238 must sign the ICF for the open-label trial before any procedures specific to Trial 331-10-238 can be performed. Subjects will retain the same subject identification (Subject ID) number assigned in the prior double-blind phase 3 trial. The following procedures need to be performed at Screening/Baseline of Trial 331-10-238; if any of these assessments were conducted at the last scheduled visit of the prior double-blind phase 3 trial, then Screening/Baseline values for those assessments will be derived from that visit and those assessments will not need to be repeated at Screening/Baseline of Trial 331-10-238.

- Inclusion/exclusion criteria for Trial 331-10-238 will be reviewed to assure the subject's eligibility.
- Medical history will be updated, if necessary, using information from the prior double-blind phase 3 trial.
- Subjects will submit to a physical examination and assessments of waist circumference, vital signs, and ECG.
- The investigator (or qualified designee) will administer the CGI-S and CGI-I.
- Subjects will complete any Baseline instrument (ie, SDS, IDS-SR, and MSFQ).
- An adequately trained and experienced clinician will administer any EPS scale (ie, SAS, AIMS, and BARS).
- The investigator (or qualified designee) will complete the “Since Last Visit” C-SSRS form.
- Concomitant medications will be reviewed to assure that the subject is not receiving any prohibited medications.
- Subjects will complete the Baseline RUF.
- For subjects entering Trial 331-10-238 after completing the last scheduled visit of the prior double-blind phase 3 trial, a fasting blood sample will be drawn for analysis of any clinical laboratory parameter (ie, the clinical laboratory parameters specified in **Table 3.6.2.1-1**) that was not drawn at the last scheduled visit of the prior double-blind phase 3 trial.
- AE recording will begin with the signing of the ICF for Trial 331-10-238.
- Trial personnel will call the interactive voice response system (IVRS) or access the interactive web response system (IWRS) to register the visit and to obtain blister card and ADT bottle number assignments. The assigned open-label brexpiprazole and ADT will be dispensed. Treatment will begin with brexpiprazole 0.5 mg/day for 1 week. The ADT will be the same as the one taken during the prior double-blind phase 3 trial. The dose of ADT should not be changed at this time.

3.6.1.2 Week 1

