3.6.2.4.4 Suicidality

Suicidality will be monitored during the trial using the C-SSRS. Subjects completed the “Baseline/Screening” C-SSRS form at the beginning of the prior double-blind phase 3 trial; therefore, only the “Since Last Visit” C-SSRS form will be used in Trial 331-10-238. A copy of the “Since Last Visit” C-SSRS form is provided in [Appendix 13](#).

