The trial will be organized as follows:

Screening/Baseline: Subjects will be screened for eligibility at the last scheduled visit of the prior double-blind phase 3 trial. Subjects will sign a separate informed consent form (ICF) for participation in Trial 331-10-238 before any procedures specific to the open-label trial are performed. The assessments from the last scheduled visit of the prior double-blind phase 3 trial will serve as the baseline measures for Trial 331-10-238 for any assessment that is not unique to the open-label trial. Medical history will be updated, if necessary.

Treatment Phase: Eligible subjects will receive daily treatment with open-label brexpiprazole and ADT as described in the Investigational Medicinal Product (IMP), Dose, Formulation, Mode of Administration section. Visits will occur at the end of Weeks 1, 2, 4, 8, 14, 20, and 26. All subjects will receive up to 26 weeks of open-label treatment in Trial 331-10-238.

Follow-up: Subjects will be followed up for safety via telephone contact or clinic visit 30 (+ 2) days after the last dose of open-label medication.

[figure not shown]

Figure 3.1-2 Trial Design Schematic

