6.3 Protocol Deviations

Protocol deviations data will be summarized by type of deviations (eg, deviations in entry criteria, dosing, concomitant medication, procedural, etc.). In addition, a patient listing will be provided describing the deviations for each subject.

7 Analysis of Demographic and Baseline Characteristics

Baseline demographic characteristics including age, race, ethnicity, gender, weight, height, and BMI will be summarized by descriptive statistics (frequency, mean, median, standard deviation, maximum, minimum, and percentage when applicable)

8 Efficacy Analysis

Efficacy is secondary objective for the study. Efficacy endpoints are as follows:

- 1) Change from baseline in CGI-S score, by trial week and at the last visit (ie, Week 26/ET or Week 52/ET);
- 2) Mean CGI-I score, by trial week and at the last visit (ie, Week 26/ET or Week 52/ET);
- 3) Change from baseline in SDS score, by trial week and at the last visit (ie, Week 26/ET or Week 52/ET);
- 4) Change from baseline in IDS-SR Total Score, by trial week and at the last visit (ie, Week 26/ET or Week 52/ET).

Descriptive statistics will be provided for each endpoint. The analysis will be carried out on the Efficacy Sample. Descriptive statistics will be summarized at each trial visit using the OC data set and at the last visit using the LOCF data set.

9 Safety Analyses

The primary safety analysis is the frequency and severity of AEs (see Section 9.1). Other standard safety variables to be analyzed include clinical laboratory tests, vital signs, ECGs, body weight, waist circumference, and BMI. In addition, data from the following safety scales will be evaluated: SAS, AIMS, BARS, C-SSRS, and MSFQ. Analyses regarding safety and tolerability will be conducted based on the Safety Sample, which is defined in Section 5.1. In general, baseline measurements of safety variables are defined as their last measurements prior to the first dose of open-label brexpiprazole.

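### SAP 9.5 judges treatment-emergent and worsened suicidality against one Since-Last-Visit C-SSRS, so recurrence of ideation or behavior recorded earlier in the parent trial is counted as emergent

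*SAP*

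**What the plan says.** SAP 9.5 plans four treatment-emergent outputs from the C-SSRS, all relative to baseline:

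- Emergence of ideation or of behavior: "report of any type of suicidal behavior/ideation during treatment when there was no baseline suicidal behavior/ideation".
- Emergence of serious ideation: "observation of suicidal ideation severity rating of 4 or 5 during treatment when there was no baseline suicidal ideation".
- Worsening: "a suicidal ideation severity rating that is more severe than it was at baseline".

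SAP 9.5 does not say which C-SSRS record is the baseline. SAP section 9 gives the default, introduced as holding in general: "baseline measurements of safety variables are defined as their last measurements prior to the first dose of open-label brexpiprazole". SAP 3.1 fixes the visit: "The assessments from the last scheduled visit of the prior double-blind phase 3 trial will serve as the baseline measures for Trial 331-10-238". It applies this to every measure that both trials collect.

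Protocol 3.6.1.1 and footnote n of Table 3.6-1 make the Screening/Baseline C-SSRS a Since-Last-Visit form. Protocol 3.6.2.4.4 gives the reason: the Baseline/Screening version was filled in once, when the parent trial started, which leaves the Since-Last-Visit version for this trial (the sentence reads in part "C-SSRS form at the beginning of the prior double-blind phase 3 trial; therefore, only the"). Exclusion 11 in protocol Table 3.4.3-1 removes subjects with ideation item 4 or 5, or any behavior item, positive at that visit. It also lets the investigator judge suicide risk "including consideration of responses on the C-SSRS throughout the prior double-blind phase 3 trial".

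**The concern.** The two sides of the comparison look back over very different spans. Baseline is one interval between visits. The on-treatment side is the worst of a chain of forms (Weeks 1, 2, 4, 8, 14, 20 and 26, and on to Week 52 before Amendment 3) that leaves no gap. Ideation that comes and goes at a constant rate will often miss the short baseline interval and be caught at some point in the long one.

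Entry selection adds to this. Eligible subjects have no suicidal behavior on the form that serves as baseline, so emergence of behavior is close to any on-treatment behavior, whatever happened earlier. Subjects with level 4 or 5 ideation on that form are excluded too, so the record used as baseline is one on which subjects were selected for a low reading.

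Safety is the primary objective and there is no control arm, so the emergent tables will be read alone. As planned, they do not show how many cases are new and how many are a return of something already on record before the open-label drug.

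**Working it through.** **Tracing the baseline.** The documents give no figure on this point, so there is none to reproduce. The chain is:

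1. SAP 9.5 names no C-SSRS baseline, so the section 9 default applies: the last record before the first open-label dose.
2. That record comes from the last scheduled parent-trial visit (SAP 3.1).
3. It is a Since-Last-Visit form (protocol 3.6.1.1; Table 3.6-1, footnote n).
4. The Baseline/Screening form dates from the start of the parent trial (protocol 3.6.2.4.4). Neither document carries it, or the intermediate parent-trial forms, into the analysis baseline.

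So no baseline ideation means none since the preceding parent-trial visit.

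**Illustration of direction.** Let p be the weekly probability of reporting ideation, the same before and during treatment and independent between weeks; w the baseline look-back in weeks; T the weeks on treatment. Then

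P(emergent) = (1 − p)^w × [1 − (1 − p)^T].

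From the documents: T = 26, and a parent trial of 14 weeks with an 8-week Phase A (Trials 331-10-227, 331-10-228 and 331-13-214). Assumed: p from 0.02 to 0.20, and w of 1 or 2 weeks, because parent-trial visit spacing is not given. The column w = 14 shows a baseline that covers the whole parent trial.

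Example, p = 0.05 and w = 2: 0.95^2 × (1 − 0.95^26) = 0.665. With w = 14: 0.95^14 × (1 − 0.95^26) = 0.359.

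| p | w = 1 | w = 2 | w = 14 |
|---|---|---|---|
| 0.02 | 0.400 | 0.392 | 0.308 |
| 0.05 | 0.700 | 0.665 | 0.359 |
| 0.10 | 0.842 | 0.758 | 0.214 |
| 0.20 | 0.798 | 0.638 | 0.044 |

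Risk is unchanged in every row. The fall from left to right comes only from the look-back.

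**Share of emergent cases that are recurrences.** This is 1 − (1 − p)^(14 − w), the probability of at least one report in the earlier weeks of the parent trial. The last column is the share that a history window limited to the 8 pre-randomisation weeks would identify, 1 − (1 − p)^8, ignoring whatever the Baseline/Screening form adds.

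| p | w = 1 | w = 2 | Identified by 8-week window |
|---|---|---|---|
| 0.02 | 0.231 | 0.215 | 0.149 |
| 0.05 | 0.487 | 0.460 | 0.337 |
| 0.10 | 0.746 | 0.718 | 0.570 |
| 0.20 | 0.945 | 0.931 | 0.832 |

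Against w = 2, the 8-week window finds 0.149/0.215 = 69% of the recurrences at p = 0.02 and 0.832/0.931 = 89% at p = 0.20.

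**Why the window must be common.** Suppose history used all parent forms for parent-placebo subjects but only pre-randomisation forms for parent-brexpiprazole subjects. With two-week periods and a period probability of 0.2, 12 weeks before the baseline interval make 6 periods and Phase A makes 4. The share of emergent cases labelled new would be 0.8^6 = 26% against 0.8^4 = 41%, at identical risk. SAP 5.1 presents all summaries by parent treatment group, so this artefact would be visible. One common window gives 41% in both groups.

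**The case against.** The rule is conventional. It matches the rest of the SAP: section 9.1 counts any AE starting after the first dose as treatment-emergent, and Table 9.4-1 defines new-onset QTc against baseline alone. Nothing in SAP 9.5 claims to identify first-ever ideation, and in an uncontrolled safety trial over-reporting is the safer error. All of that stands, and it is why the rule should be kept.

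The baseline is also partly inferred. The section 9 default is qualified as general, so a wider C-SSRS baseline is not expressly ruled out. But neither document supplies one, and the remedy for an unnamed baseline is to name it.

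A reader might go further and infer that new and recurrent cases cannot be told apart at all. The documents do not support that. CT-6.4.5 to CT-6.4.8 are subject-level listings, and protocol 3.6.1.1 states: "Subjects will retain the same subject identification (Subject ID) number assigned in the prior double-blind phase 3 trial". Cases can be traced; the plan simply does not do so. The counts in CT-6.4.1 to CT-6.4.3 do not use baseline at all.

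**Conclusion.** The asymmetry is documented and its direction is clear: the emergent and worsening outputs over-count, because recurrences after a negative or low last parent-trial form are included. It affects only subjects with such a form, and only CT-6.4.4 to CT-6.4.8.

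The size is not established. Visit spacing, report probability and the proportion of subjects with fluctuating ideation are all assumptions, and the model treats weeks as independent. The 22% to 95% range shows how strongly the answer depends on p; it is not an estimate for this trial. A reader might be tempted to quote a fixed share of emergent cases as false, or to call the suicidality result invalid. Neither follows. This is a cheap improvement to how a key safety result can be read.

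**What to change.** Amend SAP 9.5 and CT-6.4.4 to CT-6.4.8 as follows.

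1. Name the baseline record (the Since-Last-Visit C-SSRS at the last scheduled parent-trial visit) and state its look-back.
2. Keep the current definitions of emergence and worsening as the main rows.
3. Define one prior-history window for every subject, whatever the parent arm: all parent-trial C-SSRS forms up to the end of the pre-randomisation phase, including the Baseline/Screening form. For Trials 331-10-227, 331-10-228 and 331-13-214 this is Phase A through Week 8; for other parent trials, list the corresponding forms by trial, since their schedules are not in these documents.
4. For emergence of ideation, and likewise of behavior, call a case new if nothing at any level appears on those forms or at baseline. Use the subjects who meet that condition as the denominator. Other emergent cases are recurrent.
5. For worsening, report whether the on-treatment level exceeds the highest level on those forms and at baseline.
6. Footnote that ideation arising only in the parent double-blind phase is not captured as prior history.

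The cost is a merge with parent-trial C-SSRS records on the retained Subject ID, extra columns in the tables and listings, and the limitation in item 6. Trial conduct does not change.

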Has subject engaged in Non-Suicidal Self-Injurious Behavior? Interrupted Attempt: When the person is interrupted (by an outside circumstance) from starting the potentially self-injurious act (if not for that, actual attempt would have occurred). Overdose: Person has pills in hand but is stopped from ingesting. Once they ingest any pills, this becomes an attempt rather than an interrupted attempt. Shooting: Person has gun pointed toward self, gun is taken away by someone else, or is somehow prevented from pulling trigger. Once they pull the trigger, even if the gun fails to fire, it is an attempt. Jumping: Person is poised to jump, is grabbed and taken down from ledge. Hanging: Person has noose around neck but has not yet started to hang - is stopped from doing so. Has there been a time when you started to do something to end your life but someone or something stopped you before you actually did anything? If yes, describe:		Yes  No  Total # of interrupted <hr/>
Aborted Attempt: When person begins to take steps toward making a suicide attempt, but stops themselves before they actually have engaged in any self-destructive behavior. Examples are similar to interrupted attempts, except that the individual stops him/herself, instead of being stopped by something else. Has there been a time when you started to do something to try to end your life but you stopped yourself before you actually did anything? If yes, describe:		Yes  No  Total # of aborted <hr/>
Preparatory Acts or Behavior: Acts or preparation towards imminently making a suicide attempt. This can include anything beyond a verbalization or thought, such as assembling a specific method (e.g., buying pills, purchasing a gun) or preparing for one's death by suicide (e.g., giving things away, writing a suicide note). Have you taken any steps towards making a suicide attempt or preparing to kill yourself (such as collecting pills, getting a gun, giving valuables away or writing a suicide note)? If yes, describe:		Yes  No 
Suicidal Behavior: Suicidal behavior was present during the assessment period?		Yes  No 
Completed Suicide:		Yes  No 

Answer for Actual Attempts Only	Most Lethal Attempt Date:

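### The SAP 9.5 row for emergence of serious suicidal ideation omits subjects who rise from a baseline level of 1–3 to 4–5; they appear in other tables but not in that row or its listing

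*SAP*

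**What the plan says.** SAP 9.5 puts treatment-emergent suicidality into four categories: emergence of ideation, emergence of serious ideation, worsening of ideation, and emergence of behaviour. Serious emergence requires a "suicidal ideation severity rating of 4 or 5 during treatment when there was no baseline suicidal ideation". The next rule reads: "Worsening of suicidal ideation is defined as a suicidal ideation severity rating that is more severe than it was at baseline". The categories feed table CT-6.4.4. Serious emergence has its own listing (CT-6.4.7), and so does worsening (CT-6.4.8).

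Protocol Table 3.4.3-1, exclusion 11, bars subjects who answer yes at entry to item 4 ("Active Suicidal Ideation with Some Intent to Act, Without Specific Plan") or item 5 ("Active Suicidal Ideation with Specific Plan and Intent"), or to any suicidal behaviour item, or whom the investigator judges to be at serious risk. A yes on items 1–3 does not in itself exclude.

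SAP 9.5 also plans summaries of "behavior by type (4 types), ideation by type (5 types"), without naming the four behaviour types. Protocol 7.4.5 gives the same counts. The form in Protocol Appendix 13 carries a separate item, "Completed Suicide".

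**The concern.** The entry rule and the analysis rule set their thresholds at different points. Entry is closed at level 4, so the clinically natural event to count is a crossing from below 4 to 4 or 5. The SAP counts that crossing only for subjects who start at zero. A subject who enters with a passive wish to be dead and later reports a plan with intent is not counted as having emergent serious ideation.

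Baseline ideation of 1–3 is plausible here. Subjects have MDD, and those arriving from Phase A+ must not have been in remission. Baseline is rated on the since-last-visit form (Protocol 3.6.2.4.4), so one report of item 1 in that interval is enough to take a subject out of the row.

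The primary objective is safety. A reader of CT-6.4.4 or CT-6.4.7 would reasonably take the serious-ideation entries to be all new serious ideation on treatment, and they are not.

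**Working it through.** The plan states no figure to reproduce, and the sample size is not based on power. The check applies the definitions to every possible pattern.

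**Inputs**
- Levels 1–5 are the ideation items of the C-SSRS form (Protocol Appendix 13). Here 0 means that no item was endorsed.
- Eligible baseline B is 0, 1, 2 or 3 (exclusion 11). On-treatment rating is T.
- Serious emergence under SAP 9.5: T ≥ 4 and B = 0.
- Worsening under SAP 9.5: T > B.

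**Step 1: patterns that end at 4 or 5.** There are 4 baselines × 2 outcomes = 8.

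| B | T | Serious emergence | Worsening | Ideation by type |
|---|---|---|---|---|
| 0 | 4, 5 | yes (2) | yes | yes |
| 1 | 4, 5 | no (2) | yes | yes |
| 2 | 4, 5 | no (2) | yes | yes |
| 3 | 4, 5 | no (2) | yes | yes |

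The row counts 2 of 8 and omits 6. With the rule T ≥ 4 and B ≤ 3 it counts all 8. These are patterns, not subjects.

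**Step 2: whether the worsening row can stand in.** For B = 1, 2, 3 there are 4 + 3 + 2 = 9 worsening patterns. Six end at 4–5 and three do not (1 to 2, 1 to 3, 2 to 3). As worded, the rule also admits B = 0, so a shift from 0 to 1 qualifies too. The row count cannot isolate serious ideation.

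**Step 3: the SAP's convention elsewhere.** In Table 9.4-1, new onset of QTc above 500 msec means exceeding 500 during treatment but not at baseline. A subject at 470 msec at baseline who passes 500 is counted. That baseline test sits at the serious threshold, whereas the suicidality test sits at zero.

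**Step 4: size.** The documents give no rate of baseline ideation and none of reaching 4–5. Let f be the share of subjects reaching 4–5 who had B = 1–3. The row then counts a fraction 1 − f. For an assumed 20 such subjects:

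- f = 0.1: 20 × 0.9 = 18 counted
- f = 0.3: 20 × 0.7 = 14
- f = 0.5: 20 × 0.5 = 10
- f = 0.7: 20 × 0.3 = 6

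If a share p enters at 1–3 with r times the risk of the others, f = pr / (pr + 1 − p). With p = 0.15, r = 1 gives f = 0.15, and r = 10 gives 1.5 / (1.5 + 0.85) = 0.64. Both p and r are assumptions, so this shows sensitivity and is not an estimate for the trial.

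**The case against.** The strongest reply is that nothing is lost. The SAP uses its terms consistently: emergence is onset from none and worsening is any rise. Ideation by type (CT-6.4.3) is not conditioned on baseline. Because items 4 and 5 are barred at entry, its rows for those items show serious ideation on treatment whatever the baseline level. The same subjects count in overall suicidality, and the CT-6.4.8 listing lets a reader separate 1 to 2 from 3 to 5. The primary safety analysis is adverse events, not the C-SSRS. All of this stands and limits the scope. It does not make the serious-ideation row or its listing complete, and their titles give no hint of the restriction.

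Three stronger readings are tempting but unsupported.
- **That the SAP as a whole undercounts serious suicidality.** The outputs just named show otherwise.
- **That a completed suicide would be absent from the behaviour tables.** The form has actual, interrupted and aborted attempts, preparatory acts and completed suicide, which is five outcomes against four types, so omission is a possible inference. But the types are never named. The form lets several behaviours be checked, and an actual attempt carries a lethality code for death, so a suicide could be counted there. Deaths also appear in the summary of TEAEs with a fatal outcome (CT-8.4) and in the listing of deaths (CT-9.1). What remains is missing detail.
- **That every on-treatment rating of 4–5 is new.** The item-4 and item-5 bar concerns the entry visit. Ratings earlier in the parent trial matter only through the investigator's judgement.

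**Conclusion.** The point holds for one row of CT-6.4.4 and for listing CT-6.4.7. Under the SAP 9.5 wording, a rise from level 1–3 to 4–5 is not emergence of serious suicidal ideation, and within the treatment-emergent table it appears only under worsening. Two of eight eligible patterns are counted. This rests on the text alone, taking baseline as the last rating before the first open-label dose (the general rule in SAP 9) and assuming that exclusion 11 was followed. The number of subjects affected is unknown, and any percentage would come from assumed rates. It is a specific, cheap improvement to a safety table. It does not show that data are lost or that the primary analysis is affected. The completed-suicide question is a clarification and no more.

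**What to change.** In SAP 9.5, define emergence of serious suicidal ideation as an on-treatment rating of 4 or 5 with a baseline rating of 0–3. Alternatively, keep the present row, label it as restricted to subjects without baseline ideation, and add a row for shifts from 1–3 to 4–5. Apply the choice to all versions of CT-6.4.4 and CT-6.4.7 (all subjects, 52-week enrollers, 26-week enrollers).

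As a clarification, list the four behaviour types and state where a completed suicide is counted. Keep this consistent with Protocol 7.4.5, which also specifies four types; adding a fifth would be a departure from the protocol to be recorded.

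The cost is a few SAP sentences and minor reprogramming, with no new data collection. The reported count of emergent serious ideation may become less favourable.
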